Baseline covariates will be examined to determine whether randomization performed as intended. Any that are significantly imbalanced across study arms will be included in multivariate analyses.

We will use logistic regression to analyze outcomes (e.g., bullying perpetration, other aggressive behaviors; bystander behavior). Once gross estimates of intervention effect have been calculated, covariates will be added to examine

whether they appear to mediate the relation between group assignment and the outcome. Three conditions must be met in order to claim that mediation is present:⁹³⁻⁹⁵ (1) a predictor (e.g., experimental arm) is significantly associated with a mediator (e.g., TPP motivation); (2) The mediator is significantly associated with an outcome (e.g., pregnancy); and (3) when one controls for the mediator, the effect of the predictor on the outcome becomes non-significant. If this effect retains significant but is attenuated, partial mediation is indicated. A 10% or greater change in the point estimate will be deemed clinically significant.^{96,97}

Sex as a biological variable. It is possible that males will respond to the program differently than females because it feels more individual and perhaps, in this way, will resonate more with males.⁸³ Conversely, perhaps because females text message at a greater volume than males,^{36,84} the format of this program may resonate more with them. As such, sex will be explicitly examined as a potential moderator. To understand whether the intervention impact varies by sex, we will test an interaction term, i.e., experimental group X sex. If the term is statistically significant, then it will suggest that boys and girls are impacted differentially by the intervention.

To examine whether/how the intervention effect attenuates over time, we will use generalized estimation equations to analyze the data across follow-up periods using an identity link and exchangeable correlation structure. By entering an interaction term for experimental group X time, we can determine if the intervention is differently impactful at intervention end versus 3-months post-intervention.

Should [name] need statistical guidance, we will take advantage of [name] access to the biostatistics 'core' at the University of North Carolina (please see Budget Justification).

Power analysis

Because the behavioral outcomes data in this R21 will be used to inform the power analyses of the future R01, we respectfully suggest that a power analysis for this study is premature.

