3. RESEARCH PROTOCOL

3A. DESCRIPTION OF STUDY POPULATION, INCLUSION AND EXCLUSION CRITERIA

Study Sites. [name] has a strong relationship with the Chatham County School District (See Letter of Support). There are 8 middle schools in the District, with a combined enrollment of 712 7th graders. The schools are diverse in terms of race and income: 47% are racial/ethnic minority (e.g., 31.5% are Black) and 69% are receiving free or reduced cost lunch. We will randomly select three schools. Should a school choose to opt out, we will randomly select another from the remaining five schools. Note that, while enthusiasm for the program is high, it is against district policy to allow principals to provide Letters of Support.

Should additional sites be needed, we will draw upon local Boys & Girls Clubs. The Boys & Girls Club of America (BGCA) includes over 4,000 clubs in the U.S. and serves approximately 4 million young people. Local clubs affiliated with the BGCA provide young people with a safe, supervised, and constructive environment during non-school hours. The organization serves a diverse population of young people with a large representation from low-income backgrounds. The Boys & Girls Clubs of Durham and Orange Counties serve students in the cities of Durham and Chapel Hill. The clubs are diverse in terms of race and income: 85% are African American, 6% Hispanic, 3% are White, 3% are Asian, 2% are Multiracial, and 1% are American Indian/Alaskan Native. About 62% of students are experiencing financial hardship, 1% have disabilities, and 4% are English Language Learners.

We also may recruit 13-14 year olds using advertisements on social media, such as Facebook and Instagram.

Youth eligibility criteria. The inclusion criteria for youth matches the anticipated profile of users when the program is publicly available in the future. Participants will: be enrolled in one of our partner schools, be in middle school (i.e., 7th or 8th grade) or between the ages of 12-14 years of age, be English-speaking, own their own cell phone, intend to have the same cell phone number for at least 3 months (this may or may not apply, depending on the number of youth who meet this criterion), provide informed written assent, and have parental permission. Non-English speakers and youth who do not have the reading ability to complete the screener are not eligible.

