Youth recruited via social media additionally must be 13 years of age or older due to the Children’s Online Privacy Protection Act.

Justification for eligibility criteria. Excluding Spanish youth: Only 11% of students in the Chatham County School District are English language learners, suggesting that more than 600 of the 7th graders will be English-speaking.

Requiring cell phone ownership: If we gave youth phones, findings would not be generalizable (e.g., community-based organizations are unlikely to provide cell phones). **National data suggest that low income youth are as likely as higher income youth to have cell phones.**¹³ Our District contact estimates that almost all students have a cell phone. Similarly, [name] recently conducted FGs with low-income middle school students and most had a cell phone. As

such, we are not reifying the digital divide with this criterion.

3B. SAMPLE SIZE

We will include ~60 youth in focus groups, ~70 in content advisory teams, 15-20 youth in a beta test if time allows, and 150 in a randomized controlled trial.

For the focus groups, we will enroll about 60 youth to take part in the online discussion. The groups will be stratified by characteristics that we posit will contribute to a sense of shared experiences and/or affect the likelihood of being a perpetrator of bullying. This may include sex, race/ethnicity, among others. We will endeavor to purposefully sample youth so that at least 50% are racial/ethnic minority, at least 50% are receiving free or reduced cost lunch, at least 30% report bullying perpetration and 30% report bullying victimization (note that there may be overlap such that a youth is both a bully and a victim). Actual distributions of youth who screen eligible may result in different ratios. We anticipate partnering with about 7 schools and about 2 BCGA Clubs. We will work with school administrators and Club Directors to determine the optimal school participation for each research activity.

3C. DESIGN AND DESCRIPTION OF METHODOLOGY

Recruitment and enrollment protocol

In person recruitment.

Recruitment and enrollment will be similar for each of the three research activities. Chatham County Public School administration has agreed to dedicate classroom time for us to recruit youth from middle schools. We also will recruit from local Boys & Girls Clubs and via social media.

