Integrating lessons learned into the content. Several participants in the beta test expressed confusion regarding the interactive Text Buddy feature. Further probing revealed that some of this was related to feelings of discomfort about discussing bullying with students they went to school with. Nonetheless, beta test participants sent between 0-52 messages to their Text Buddy, suggesting its acceptability potential. To improve the experience, we will expand the instructions for the Text Buddy feature and include more concrete prompts about what Buddies can talk about with each other (e.g., Maybe text your buddy and talk about what you think it would be like if you stood up for a friend being bullied at school tomorrow). We also will match youth with someone at a different school/setting and make sure that they are aware of this so they do not worry they are talking with a classmate they may know.

Drafting attention matched control content. In the beta test, the control group received two messages a week focused on thanking them for being in the study. As has been done in [name] other interventions (e.g., R21 CA135669; R34MH109296), we will draft attention-matched content to well position this R21 for a competitive R01 submission. To ensure that youth in both arms receive the same 'attention,' content will address healthy lifestyle topics unrelated to bullying (e.g., fitness, nutrition).

Confirming adapted content for acceptability in Content Advisory Teams (CAT; n=70). The content will next be reviewed by a CAT comprised of ~24 students. Each CAT member will have one week to review the messages and provide feedback through an online platform. Next, an online group discussion will elicit reactions to the messages and program design. Possible questions include: How well do these messages speak to the experiences you and your friends have around bullying? How clear do you find the messages? How could we say things differently to make the messages more understandable? Once feedback from the CAT has been integrated, a second 24-member CAT of different students will confirm that the content has been improved. For instance, in a previous intervention development [name]'s team led, the second CAT noted that we included too many emojis, which we had added based upon feedback from the first CAT. Having two different groups review the content also ensures a wider range of opinions and feedback. The control content will be reviewed by a ~24-member CAT.

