Conducting a beta test to confirm the protocol, including the software functionality and surveys. Before rolling out the RCT, we may conduct a beta test to pilot the recruitment, enrollment, data collection, and randomization procedures, as well as to identify final opportunities to improve the content. In most cases, five is a sufficient number of testers to identify any issues. Here, we propose 15-20 youth so that ~10 youth will test the functionality of the intervention program and ~5 the functionality of the control program. Usability data will be collected weekly via text messaging from participants. We may send questions weekly via text messaging, or by phone for non-responders, about the program experience. At the end of the beta test, we may conduct one-on-one interviews to identify any additional experiential issues that need to be addressed before the RCT is launched.

Pilot RCT of BullyDown (n = 150)

Randomization and group assignment. Once youth complete the baseline survey, they will be randomly assigned to either the intervention (n = 76) or the control (n = 74) group. We will use a computerized minimization technique, as originally described by Taves⁵⁹ and more recently reviewed by others,⁶⁰⁻⁶² to balance the sample on youth key indicators. These may include sex, school or Club, and bullying perpetration history. Treatment assignment will be generated and maintained at a password-protected Internet website monitored by [name].

Contamination. Studies across participant populations and behavioral targets report that contamination is uncommon and does not affect study outcomes.^{63,64,65,66} Give this, and to be efficient with R21 resources, students will be randomized at the individual rather than school or Club level. As we have done previously,^{63,64} we will ask questions at intervention end that are specific to the BullyDown content. If indicated, we will include the number of correct exposure

questions as a proxy for contamination in multivariate models.

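### The eligibility rules do not keep youth who have already reviewed or received BullyDown out of the RCT

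*Combined protocol and SAP*

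**What the plan says.** All references are to the combined protocol and SAP.

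- **Who is eligible (3A).** Youth must "be in middle school (i.e., 7th or 8th grade) or between the ages of 12-14 years of age", and meet language, phone, assent and permission conditions. The only stated exclusions are: "Non-English speakers and youth who do not have the reading ability to complete the screener are not eligible". For online recruits one rule is added: "Youth recruited via social media additionally must be 13 years of age or older". Earlier BullyDown participation is not mentioned.
- **How they are found (3B, 3C).** "Recruitment and enrollment will be similar for each of the three research activities". The sources are schools, Clubs and social media. In the focus-group paragraph of 3B: "We anticipate partnering with about 7 schools and about 2 BCGA Clubs". The split of schools between activities is left open: "We will work with school administrators and Club Directors to determine the optimal school participation for each research activity". For in-person recruitment, RCT youth are then drawn at random from those who screen eligible.
- **Who sees content before the RCT (3C, Specific Aim 1).** Two CATs of about 24 review the BullyDown messages, and a third of about 24 reviews the control content. "Each CAT member will have one week to review the messages and provide feedback through an online platform". For the optional beta test: "Here, we propose 15-20 youth so that ~10 youth will test the functionality of the intervention program", with about 5 more on the control program.
- **Non-overlap rules.** The only one is that the second CAT must be made up of other youth than the first.
- **Exposure check (3C, Contamination).** Questions specific to BullyDown content are asked at intervention end and may enter multivariate models if that seems indicated.

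**The concern.** A recruiter applying section 3A as written would pass a former CAT member or beta tester as eligible, and the allocation program could place that youth in either arm. Three things are at stake.

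1. **Acceptability**, a main outcome, is judged by whether mean ratings reach 4 on a 5-point scale (3E). Youth who commented on the messages, or tested the program, are not naive raters of it.
2. **The behavioural contrast**, meant to inform power for the R01, is diluted if some controls have already read BullyDown material and retained something from it.
3. **The contamination check** cannot tell prior exposure from leakage during the trial. Controls who learned the content in a CAT would answer correctly and could be counted as evidence of cross-arm contamination.

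**Working it through.** **Consistency of the plan's own counts.** Arms: 76 + 74 = 150, as stated. CATs: 3 x 24 = 72, against about 70 stated. English-speaking 7th graders: 712 x (1 - 0.11) = 634, against more than 600 stated. These agree. The plan gives no overlap figure and no power calculation to reproduce.

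**Youth with prior BullyDown exposure.** Two intervention CATs: 24 + 24 = 48. Beta-test intervention group, if run: about 10. Total about 58.

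**Expected overlap.** If K exposed youth sit in an eligible pool of N and are as likely as others to enrol, the expected number in the RCT is 150 x K/N, of whom 76 x K/N are in the intervention arm and 74 x K/N are controls. K and N depend on assumptions, because the documents give neither a timetable nor a school allocation:

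- N = 634 takes one cohort of 7th graders. N = 1,268 adds an 8th grade of equal size (assumed), as would be needed if a school year passes between development work and RCT.
- K is halved if only half of the exposed youth come from the district or remain eligible.

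| K | N | Share | Of 150 | Intervention | Control |
|---|---|---|---|---|---|
| 58 | 634 | 9.1% | 13.7 | 7.0 | 6.8 |
| 58 | 1,268 | 4.6% | 6.9 | 3.5 | 3.4 |
| 29 | 634 | 4.6% | 6.9 | 3.5 | 3.4 |
| 29 | 1,268 | 2.3% | 3.4 | 1.7 | 1.7 |
| 48 (no beta test) | 634 | 7.6% | 11.4 | 5.8 | 5.6 |
| 24 (half of 48) | 1,268 | 1.9% | 2.8 | 1.4 | 1.4 |

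The range is therefore about 3 to 14 of 150, or 2-9%. Under simple random sampling the chance of at least one overlap is 97.5% or more in the first four rows. That chance does not apply if development and RCT schools are kept apart.

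**Behavioural contrast (illustration, upper bound).** Assume 22% bullying in unexposed controls (midpoint of the 20-24% in section 1), 12% under BullyDown (assumed), and full carry-over in exposed controls. With exposed share f, the control rate is 0.22 - 0.10f and the risk difference is 0.10 x (1 - f):

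- f = 2.3%: 9.8 points
- f = 4.6%: 9.5 points
- f = 9.15%: 9.1 points

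Sample size per arm for a future trial planned on those rates (two-sided 5%, 80% power, normal approximation with pooled variance under the null) goes from 221 with no overlap to 240 at 4.6% and 262 at 9.15%.

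For scale, the standard error of the pilot's risk difference at these rates is sqrt(0.22 x 0.78/74 + 0.12 x 0.88/76) = 0.061, or 6.1 points. The largest shift above, 0.9 points, is about 0.15 of that.

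**Acceptability (illustration).** If exposed youth rate the program 0.5 to 1.0 points higher (assumed in size and direction), the mean moves by f times that amount: 0.046 x 0.5 = 0.02 up to 0.0915 x 1.0 = 0.09. A true mean of 3.95 among naive raters would appear as 4.04 in the highest case; a true mean of 3.90 would appear as 3.99 and still miss the threshold.

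**The case against.** The strongest reply is that the documents permit overlap but do not predict it. School participation is to be settled activity by activity, so separate schools may be used. The figure of about 7 schools stands in the focus-group paragraph and is not tied to the district's 8. Clubs and social media widen the pool, and a similar recruitment process need not mean the same youth. The beta test is optional. All of this stands, and it is why the size is a conditional range. None of it is a participant-level rule.

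Some stronger readings are tempting but not supported:

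- **That about 9% overlap is to be expected.** This needs all activities in one 7th-grade cohort, all 58 exposed youth in the district, and the beta test run. If instead a CAT member re-enters a year later as an 8th grader, the pool must include the 8th grade and the figure drops to about 7 of 150 or fewer.
- **That a pre-exposed control has in effect received the intervention.** CAT members review messages over one week. They do not get the 7-week program or its Text Buddy, and the first CAT sees text that is later revised. Full carry-over is an upper bound.
- **That arms are confounded.** Allocation follows baseline, so prior exposure is balanced in expectation. It is not a named minimization factor, so chance imbalance is possible, but the expected effect is attenuation.
- **That the planners recognised carry-over and then ignored it.** The use of new youth in the second CAT is justified by confirming improvement and widening the range of opinion, not by carry-over.
- **That all earlier participants must be barred.** Focus groups discuss peer experience before the content is updated, and the previous 22-student beta test was in Illinois, so it is not a realistic source of overlap with these schools or local Clubs.

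The exposure questions give partial protection. They would register retained knowledge by any route and can be adjusted for. But they come after randomization, are used only if indicated, and do nothing for the acceptability mean.

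**Conclusion.** The omission is certain on the text: as written, youth who have reviewed or received BullyDown can be randomized to either arm. Its consequence is minor to moderate. If exposed youth come from the district pool and enrol like others, about 3 to 14 of 150 (2-9%) would be pre-exposed, about half of them controls. The number is lower, possibly zero, if separate schools, new Clubs or social media supply the RCT, and higher if the same keen youth volunteer again.

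At these shares, dilution is at most about 1 percentage point on the assumed rates. That is small against the pilot's own imprecision, though it would carry into the R01 planning figures. The acceptability shift matters only when the mean lies close to 4. The event rates, carry-over, rating uplift, size of the 8th grade and share coming from the district are assumptions, not document figures. The point is worth acting on because unrecorded prior exposure is hard to reconstruct after enrolment.

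**What to change.** Add to the youth eligibility criteria in 3A: *Youth who took part in a BullyDown Content Advisory Team or in the new beta test are not eligible for the RCT.* Enforce it before the random draw by matching screener contact details (phone, email) to the study's own participant records; section 4.e says identifying information is retained for the duration of the study. A disguised screener item can back this up for changed numbers. Count those screened out as ineligible in the feasibility tallies.

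For focus-group youth, record prior participation at screening and run a sensitivity analysis without them; exclusion is not needed.

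**Cost.** About 58 candidates with BullyDown exposure are lost, leaving about 634 - 58 = 576 English-speaking 7th graders before 8th graders, Clubs and social media are counted. If the wording also covers control-content reviewers and beta-test controls (24 + 5 = 29), about 87 are lost and about 547 remain. Section 3C expects more eligible youth than places. Section 4.b reports that only half of active permission forms were returned in the Clubs, so that surplus should not be assumed everywhere, but a loss of 60 to 90 is still small against the pool.

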2. STUDY PURPOSE AND RATIONALE

This R21 proposal is an extension of our development work with BullyDown, a text messaging-based bullying prevention program designed for middle school students.^{19,20} Guided by the Social-Emotional Learning (SEL) model,²¹⁻²⁵ the intervention content and program features have been iteratively refined within ongoing feedback from middle school youth from across the country. The program was then beta tested with 22 middle school students in Illinois. Nine in 10 said they liked the program, and all intervention participants said that it equipped them with skills needed to not bully others in the future. Although the sample size is too small to be anything but descriptive, rates of bullying dropped from 3 youth to 1 youth in the intervention while no change was noted in the control group (2 youth at both baseline and follow-up).

Building upon our promising findings, we propose to further develop and then pilot test BullyDown in a randomized controlled trial (RCT) of middle school students. Our multidisciplinary team includes expertise in text messaging-based behavior change intervention development and evaluation ([name]), school-based evaluations of bullying prevention programming ([name]), and the psychosocial challenges associated with bullying (Drs. [name] and [name]). Together, we aim to:

Specific Aim 1: Finalize the BullyDown program. Feedback from the beta test suggest that some program features could be better described and implemented. We also will update program content to acknowledge the growing infusion of technology in the classroom, and the online interactions that it requires. Currently, almost all youth in the United States are engaging in some type of online schooling experience because of Covid-19 restrictions. Even when these are lifted, however, technology will continue to be a central feature of the way education is delivered.

To finalize the content, we will first conduct focus groups (FGs) to understand how young people are interacting with each other online, their opportunities for positive and negative communications, and whether and how teachers fit into this picture. Once the intervention content is updated, we will have youth review the messages in Content Advisory

Teams to ensure that they are understandable and salient. We also may test the program in a beta test with 15-20 middle school youth.

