Data collection. Measures will be collected online at baseline, intervention end, and 3 months post-intervention end. All participants, regardless of study condition, will complete assessments at each time point. Youth will be able to complete the surveys on their own (e.g., at home). If they are attending the brick and mortar school or Club, they also will be able to complete the survey at school or Club in the computer lab if they would prefer. To facilitate self-completion, youth will receive an invitation text message with a unique URL to access the survey. This allows participants to complete the survey at a time and place convenient for them. Alternatively, they can sign up for one of the survey sessions at school or Club that the research staff will schedule with the school or Club administration. To avoid unintentional influence that school and Club staff may have on youth survey answers, only research staff will be present in the computer lab during survey administration.

3D. MEASUREMENTS AND STUDY INSTRUMENTS

Most of the proposed measures below were used in the beta test, suggesting the survey length can be feasibly completed by adolescents in middle school or between the ages of 12-14 year of age. Measures are as follows:

Table 3. BullyDown assessment measures		
Main Outcome measures (intervention end)	Acceptability	We will measure intervention acceptability and tolerability ⁶⁷ with a combination of open-ended questions (e.g., “What aspect of the program did you like the least?”) and questions that form a scale of intervention acceptability (e.g., I liked my Text Buddy; $\alpha = .87$). Participants will estimate the number of messages they received in the past week and percent that they read. The program will record the number of weekly level-up questions answered, and the number answered correctly, as well as the number of Text Buddy and Forever Friend messages sent.
	Feasibility	We will monitor the number of eligible/ineligible youth, the number of parental permission forms received, the number of youth invited but who decline to take part, and the retention rate.

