Transcripts of the FGs will be entered into Dedoose (formerly EthnoNotes),⁸⁵ a mixed methods analysis program. Codes will be generated based on the first FG, reexamined, and refined through constant comparison with the second FG.⁸⁶ A codebook will be created with codes, brief descriptions, and illustrative quotations.⁸⁷ Codes will be both generated inductively and derived from our initial research questions (e.g., how youth interact with their peers and their teacher online). [name] project coordinator and [name] graduate research assistant will code both FGs. To assure inter-coder reliability, we will calculate a kappa value and accept a minimum of 0.75 as the criterion for adequate agreement between coders.⁸⁸ After coding is complete, we will extract themes using an iterative process to highlight evidence contradictory to our conclusions as well as the modal response.⁸⁹ The analysis will result in a report that describes the findings and advises how to integrate them into program content.

Specific Aim 2: Pilot test the 7-week BullyDown intervention for feasibility and acceptability in an RCT of 150 adolescents either in middle school and/or 12-14 years of age.

The **feasibility** of the BullyDown intervention will be determined by our recruitment and retention rates. If at least 75% of eligible studies assent and 80% complete the survey at 3-months post-intervention, we will deem these data points as supportive of a hypothesis of feasibility.

The **acceptability** of program features (e.g., badges, Text Buddy) will be measured using 5-point Likert scales; average scores of 4 or more will be supportive of acceptability.⁹⁰ Youth engagement with the program will be examined to identify potential trends in greater intervention impact (e.g., for those who use the Text Buddy feature).

Post-intervention one-on-one interviews to illuminate the intervention experience will be analyzed using a thematic approach,⁹¹ as our aim will be more descriptive in nature, with a lower level of interpretation needed than is afforded by grounded theory or other qualitative analytical techniques.⁹²

Analyses examining **behavioral outcomes** will be primarily intended to inform power analyses for the larger R01. Data will be treated as intention-to-treat and complete case. We will conduct sensitivity analyses (e.g., missing = bullying behavior) to understand how this may affect our findings. Missing data that are not the main outcomes will be imputed.

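### The conditional contamination adjustment uses a post-randomisation score that BullyDown itself should raise, so the adjusted arm coefficient is not a contamination-corrected effect

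*Combined protocol and SAP*

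**What the plan says.** Youth are randomised individually, 76 to BullyDown and 74 to control (3C, Randomization and group assignment; Contamination). To watch for leakage, "we will ask questions at intervention end that are specific to the BullyDown content". The rule for using the answers is one sentence, broken by a page: "If indicated, we will include the number of correct exposure" "questions as a proxy for contamination in multivariate models". It gives no trigger, no coding and no restriction by arm, and does not say what the adjusted coefficient estimates. Section 3E does not return to contamination.

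Other places bear on how the score would behave:
- 3C, Data collection: "All participants, regardless of study condition, will complete assessments at each time point".
- 3C, on the control messages: "content will address healthy lifestyle topics unrelated to bullying". Intervention youth receive four BullyDown messages a day for seven weeks (section 2, Specific Aim 2).
- 3D, Table 3, lists a related but separate measure under acceptability: "The program will record the number of weekly level-up questions answered, and the number answered correctly".
- 3E, Specific Aim 2: behavioural outcomes are analysed by intention to treat with logistic regression. A gross effect is calculated first, and covariates are then added to look for mediation. The main use of these analyses is to supply the R01 power calculation.

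**The concern.** A correct answer means different things in the two arms. In a control youth it may signal leakage; in an intervention youth it shows that the programme was received and understood. A single slope over both arms treats the two alike. The model then compares arms among youth with equal scores, for example an intervention youth who absorbed little with a typical unexposed control. Randomisation does not protect that comparison.

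The plan's rationale makes an effect through content plausible. Beta-test participants said of the programme that "it equipped them with skills needed to not bully others in the future", and 3E states that "Youth engagement with the program will be examined to identify potential trends in greater intervention impact". If content carries the effect, holding the score fixed removes part of what is being estimated. Section 3E would read attenuation after adding a covariate as mediation, so the same pattern could be reported under two labels.

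At stake is the behavioural effect size passed to the R01. No section says whether the estimate with or without the score is carried forward.

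**Working it through.** There is no figure of the plan's to reproduce: 3E declines a power analysis and states no effect size. The check is of structure, followed by illustration.

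**Structure.** The model in question is logit P(bullying) = a + b·arm + c·score. The coefficient b equals the randomised effect only if the score neither carries the effect nor shares a cause with bullying. Nothing in the documents secures either condition.

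**Assumed inputs (not in the documents).** 5 to 10 questions; 30% correct if unexposed and 70% if exposed; within-person correlation of answers 0.1 to 0.2; 90% of the intervention arm receives the content; 10 to 20% of controls contaminated; true odds ratio 0.50 for receiving the content. The control bullying rate is 22%, the midpoint of the 20–24% in section 1. That figure is per semester, not the 30-day outcome of Table 3; rates of 10 to 35% move the example odds ratios by 0.01 or less.

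**Example: 10 questions, correlation 0.1, 10% contamination.**

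1. Mean score: intervention 10 × (0.9 × 0.7 + 0.1 × 0.3) = 6.6; control 10 × (0.1 × 0.7 + 0.9 × 0.3) = 3.4. With equal arms, 0.9/(0.9 + 0.1) = 90% of exposed youth are in the intervention arm, so the score mostly records uptake.
2. Unadjusted odds ratio if the effect follows exposure. Unexposed odds are 0.22/0.78 = 0.2821; exposed odds 0.1410, a risk of 0.1236. Control risk: 0.9 × 0.22 + 0.1 × 0.1236 = 0.2104. Intervention risk: 0.9 × 0.1236 + 0.1 × 0.22 = 0.1332. Odds ratio: (0.1332/0.8668)/(0.2104/0.7896) = 0.577.
3. Fitting the logistic models to the exact arm-by-score distribution, with no shared cause, gives these odds ratios:

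| Effect follows | No score | Score, both arms | Raw score, controls only |
|---|---|---|---|
| Exposure | 0.577 | 0.667 | 0.506 |
| Learning | 0.580 | 0.826 | 0.409 |
| Arm alone | 0.500 | 0.500 | 0.500 |

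Share of the log odds ratio left with the both-arm score: ln 0.667/ln 0.577 = 74%; ln 0.826/ln 0.580 = 35%.

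**Over the assumed ranges.** With the both-arm score, 0.58–0.61 becomes 0.63–0.72 (exposure) and 0.58–0.62 becomes 0.75–0.90 (learning). The standard error is 1.09 to 1.30 times larger, even where the estimate does not move. The raw control-only score gives 0.49–0.53 (exposure) and 0.39–0.45 (learning).

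**A second set of assumptions.** 10 questions; 70% against 30% correct; 0 or 20% of controls contaminated, with 50% correct; bullying 22% against 11%, so (0.11/0.89)/(0.22/0.78) = 0.44. The both-arm score gives 0.43–0.44 if none of the effect runs through it, 0.66–0.67 if half does and 1.00 if all does. At 76 and 74 youth the standard error rises from 0.47 to 0.71–0.72, about 1.5 times.

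**Adding a shared cause.** Suppose an unmeasured trait shifts the score by 0.5 logit per SD and bullying by 0.25 to 0.5 log-odds per SD, in the 10-question, 10% contamination setting. With the effect through arm alone, 0.51 becomes 0.60–0.72 if the trait lowers bullying, but 0.42–0.36 if it raises it. With the effect through exposure and a trait that raises bullying, 0.58–0.59 becomes 0.57–0.49. The control-only score then ranges from 0.34 to 0.76 against a true 0.50. Under the second set, a trait that raises the score and lowers bullying takes the both-arm odds ratio to 0.76–0.85 (none through the score), 1.12–1.27 (half) or 1.71–1.88 (all).

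**Against pilot noise.** At 80% retention (0.8 × 76 ≈ 61; 0.8 × 74 ≈ 59) the unadjusted standard error is 0.51–0.52 in the example. The shifts are (0.550 − 0.405)/0.51 ≈ 0.3 SE for exposure and (0.545 − 0.191)/0.52 ≈ 0.7 SE for learning.

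**R01 illustration only.** The two-proportion formula (80% power, two-sided 5%, control rate 22%, individual randomisation) gives 361 to 367 per arm from the unadjusted odds ratios, 633 from 0.667 and 2,648 from 0.826.

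**The case against.** The strongest reply is that contamination means exposure of control youth, so the authors may intend the score for controls only. They say the questions follow their earlier practice and cite two studies, which may define the coding but cannot be consulted here. This stands as a reading: the text does not commit to one slope over both arms. It does not rescue the rule, because a control-only score comes close to the truth only when the effect follows exposure and no cause is shared.

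The step is also conditional, and the plan cites studies in which contamination was uncommon. Analysis is by intention to treat with a gross estimate first, and behavioural outcomes are labelled preliminary in a pilot whose main outcomes are feasibility and acceptability. All of this stands and limits severity. So does the noise: an interval around 0.577 at the pilot's size runs from about 0.21 to 1.58, wider than either shift.

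The support for a content path is suggestive only. The beta-test statement is self-report from a 22-youth test, 3E merely looks for trends, and level-up questions are a different measure.

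A reader might infer that the adjustment must pull the effect towards the null. The documents do not support that: it needs an effect through content, and a shared cause can move the estimate either way or past 1. A reader might equally infer that an effect through arm alone costs only precision. That too fails once a cause is shared.

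**Conclusion.** The point holds as one of unsound and incomplete specification. If triggered and entered over both arms, the score does not yield a contamination-corrected effect. Precision is lost (standard error about 1.1 to 1.3 times larger under the first assumptions, about 1.5 under the second), and the arm estimate is unshifted only if the score neither carries the effect nor shares a cause with bullying. Restricting the score to controls does not make it dependable.

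The structural conclusion needs no numerical assumption; every odds ratio above does. It would be tempting to conclude that the R01 will be mis-sized, or that the trial's main result is at risk. Neither follows: the sample sizes are illustrative, the plan does not say the adjusted estimate will be carried forward, and feasibility and acceptability are untouched. Severity is modest, and this is a cheap improvement.

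**What to change.** - Do not enter the exposure score in the models that estimate the intervention effect.
- State in 3E that the comparison by randomised arm without the score is the behavioural estimate carried to the R01.
- Report the score by arm, and judge contamination from control-arm scores only, against a cut-off fixed in advance that allows for guessing and prior knowledge.
- Label any contamination-adjusted or complier-average model as an exploratory sensitivity analysis, with its trigger, coding and assumptions stated.

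The cost is SAP wording; no new data are needed. The downside is that no model-based contamination correction is reported by default.
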